- Baseline of safety data will be defined as the last non-missing measurement prior to the first dose of study treatment. For laboratory data, any assessments made on day 1 will be considered pre-dose. If there are two visits equally eligible to assess patient status at baseline (e.g. screening and baseline assessments both on the same date prior to first dose with no washout or other intervention in the screening period) with assessment time missing, the average can be taken as a baseline value. For non-numeric laboratory tests (i.e. some of the urinalysis parameters) where taking an average is not possible then the best value would be taken as baseline as this is the most conservative. In the scenario where there are two assessments on day 1, one with time recorded and the other without time recorded, the one with time recorded would be selected as baseline.

Where safety data are summarized over time, study day will be calculated in relation to date of first treatment. When PRO data are summarized over time, study day will be calculated in relation to date of randomization.

Missing safety data will generally not be imputed. However, safety assessment values of the form of "< x" (i.e. below the lower limit of quantification) or > x (i.e. above the upper limit of quantification) will be imputed as "x" in the calculation of summary statistics but displayed as "< x" or "> x" in the listings.

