4.2.11 Patient reported outcomes

4.2.11.1 EORTC QLQ-C30 and **QLQ-LC13**

The PRO endpoints identified as primary are the following 5 lung cancer symptoms:

- Dyspnea: multi-item scale based on 3 questions ("Were you short of breath when you rested; walked; climbed stairs" QLQ-LC13)
- Cough: 1 item ("How much did you cough?" QLQ-LC13)
- Chest pain: 1 item ("Have you had pain in your chest" QLQ-LC13)
- Fatigue: multi-item based on 3 questions ("Did you need rest; Have you felt weak; Were you tired" QLQ-C30)
- Appetite loss: 1 item ("Have you lacked appetite" QLQ-C30)

The physical functioning, role functioning and GHS/QoL domains of the EORTC QLQ-C30 are furthermore pre-specified endpoints of interest.

Mixed-model repeated measures (MMRM) analysis

Change from baseline, using the MMRM analysis, will be examined for dyspnea, cough, and chest pain scores as assessed by the EORTC QLQ-LC13, and GHS/QoL, physical functioning, role functioning, fatigue and appetite loss as assessed by the EORTC QLQ-C30 and as detailed above. The MMRM analysis will examine the change from baseline in the scores for each assessment time point up to PD, death or 24 months. The analysis will be to compare the average treatment effect from the point of randomization until PD, death or 24 months unless there is excessive missing data (defined as missing in >75% of randomized patients in any treatment arm).

It is acknowledged that patients will discontinue treatment at different timepoints during the study and that this is an important time with regards to symptoms and GHS/QoL data collection. To account for this, and to include the discontinuation and follow up visits, a generic visit variable will be derived for each patient in order that the average treatment effect can be analyzed using the above method. Each visit will be assigned a sequential number. The time from randomization to each of these will be derived to select only those visits occurring within the first 24 months of randomization.

As an example, say a patient X attends the first 4 scheduled visits of a weekly schedule and then discontinues treatment, whilst patient Y discontinues treatment after the first scheduled visit, the first 6 generic visits would be as shown in Table 8:

Table 8 Generic visit variable for MMRM analysis

Generic visit	Study day (week)		
	Patient X	Patient Y	
Baseline	Baseline	Baseline	
1	8	7	
2	15	11 (discontinuation)	
3	22	22	
4	29	29	
5	33 (discontinuation)	36	
6	43	43	

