The MMRM model will include the fixed, categorical effects of treatment, visit, and treatment-by-visit interaction, TNM stage (I/II versus III) and receipt of PCI (yes versus no) as well as the continuous fixed covariate of baseline score and the baseline score-by-visit interaction. Restricted maximum likelihood (REML) estimation will be used. An overall adjusted mean estimate will be derived that will estimate the average treatment effect over visits giving each visit equal weight. For this overall treatment comparison, adjusted mean estimates per treatment group and corresponding 95% CIs will be presented along with an estimate of the treatment difference, 95% CI and p-value.

An unstructured covariance matrix will be used to model the within-patient error and the Kenward-Roger approximation will be used to estimate the degrees of freedom. If the fit of the unstructured covariance structure fails to converge, the following covariance structures will be tried in order until convergence is reached: toeplitz with heterogeneity, autoregressive with heterogeneity, toeplitz, autoregressive and compound symmetry.

Multiple imputation techniques for missing values may be considered to explore the robustness of any treatment effect.

Time to deterioration

Time to symptom, functioning and GHS/QoL deterioration will be analyzed for each of the symptom scales/items, functional scales, and GHS/QoL in EORTC QLQ-C30 and QLQ-LC13. This will be achieved by comparing between treatment groups using a stratified log-rank test as described for the primary analysis of PFS. The HR and 95% CI for each scale/item will be presented graphically on a forest plot.

For each of the symptom scales/items, functional scales, and GHS/QoL, time to deterioration will be presented using a Kaplan-Meier plot. Summaries of the number and percentage of

patients experiencing a clinically meaningful deterioration or death and the median time to deterioration will also be provided for each treatment group.

Symptom and function and GHS/QoL improvement rate

A summary of the symptom improvement rate for all symptom scales/items in EORTC QLQ-C30 and QLQ-LC13 will be produced. Similarly, a summary of improvement rate for each of the 5 function scales (physical, role, emotional, cognitive, and social) and GHS/QoL will be produced.

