- For any assessments where the visit schedule changes from $q1w \pm 3$ days to $q4w \pm 3$ days, the maximum time between two consecutive assessments is 3+7+28+3=41 days
- For any assessments where the visit schedule is $q4w \pm 3$ days, the maximum time between two consecutive assessments is 3+28+28+3=62 days

^{*}Missed visits are allowed in between assessments confirming deterioration and confirmation of deterioration requires at least 14 days between assessments (which should take into account the weekly assessment schedule for the QLQ-LC13 for the first 8 weeks).

Length of 2 missed visit window for EORTC QLQ-C30

The scheduled visit assessments and visit windows for the QLQ-C30 are 4 weekly (±3 days) relative to randomization until study termination, PFS2 or death.

Missing baseline or within 2 visits of baseline:

- A patient without baseline will be censored at day 1 unless they die \leq day 59.
- Any assessment ≤ day 59 is within 2 visits (8 weeks + 3 days) of baseline and therefore cannot be censored for missing visits.

Schedule: q4w:

• For any assessment > day 1 the visit schedule is $q4w \pm 3$ days and thus the maximum time between two consecutive assessments is 3+28+28+3=62 days (8 weeks + 6 days).

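### The PRO mixed model labels visits by each patient's own sequence rather than by scheduled week, and the SAP does not say that a missed assessment keeps its label

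*SAP*

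**What the plan says.** SAP 4.2.11.1 explains that patients stop treatment at different times and that, "to include the discontinuation and follow up visits, a generic visit variable will be derived for each patient". The rule is then: "Each visit will be assigned a sequential number". Time since randomization enters once, as a cut-off: "The time from randomization to each of these will be derived to select only those visits occurring within the first 24 months of randomization". Table 8 illustrates the variable with two patients on a weekly schedule.

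The label goes directly into the model: "The MMRM model will include the fixed, categorical effects of treatment, visit, and treatment-by-visit interaction". The overall treatment estimate averages over visits with equal weight.

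Elsewhere the documents tie PROs to the time since randomization:

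- SAP 4.1.2 sets windows by actual assessment date for by-visit presentations and adds: "When PRO data are summarized over time, study day will be calculated in relation to date of randomization". Nothing in 4.2.11.1 links the mixed model to these windows.
- SAP Appendix B says that the scheduled "visit windows for the QLQ-C30 are 4 weekly (±3 days) relative to randomization until study termination, PFS2 or death". The QLQ-LC13 is weekly for 8 weeks and every 4 weeks thereafter.
- Protocol Tables 1 and 2 give the same schedule during and after treatment. Neither lists a PRO triggered by discontinuation. Protocol 8.1.3.5 has all post-baseline forms completed away from the site.

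**The concern.** The sequential number answers a need that this trial does not appear to have. Forms fall due at the same weeks from randomization whether or not the patient is still treated, so stopping treatment creates no off-schedule PRO to fit in. What the number can do is lose track of time. If it counts only completed forms, a gap closes up and every later score takes the label of an earlier scheduled week. A missing value, which a repeated-measures model can handle under its usual assumptions, becomes a mistimed value in the visit and treatment-by-visit terms.

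Protocol 9.5.1.9 makes this model the main PRO analysis. It covers eight scores: three from QLQ-LC13 and five from QLQ-C30. Two programmers could reasonably code the rule differently.

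**Working it through.** **1. The plan's own example.** The scheduled day for weekly label k is 7k + 1.

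| Label | Scheduled day | X (offset) | Y (offset) |
|---|---|---|---|
| 1 | 8 | 8 (0) | 7 (−1) |
| 2 | 15 | 15 (0) | 11 (−4) |
| 3 | 22 | 22 (0) | 22 (0) |
| 4 | 29 | 29 (0) | 29 (0) |
| 5 | 36 | 33 (−3) | 36 (0) |
| 6 | 43 | 43 (0) | 43 (0) |

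Table 8 is reproduced if the discontinuation assessment (X day 33, Y day 11) takes the place of the next weekly form. The largest offset is 4 days and nothing carries over. If the discontinuation assessment were an additional visit and all weekly forms were also completed, sequential numbering would give X 8, 15, 22, 29, 33, 36 and Y 7, 11, 15, 22, 29, 36, which is not Table 8. The table would also arise if X missed day 36 and Y missed day 15. It therefore does not settle how a missed form is numbered.

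**2. Effect of one missed form if only completed forms are numbered.** The model runs to 24 months: 24 × 30.4375 = 730.5 days, or 104.4 weeks. That gives 8 + (104 − 8)/4 = 32 QLQ-LC13 slots and 104/4 = 26 QLQ-C30 slots. Missing the week 2 QLQ-LC13 moves labels 2 to 7 by 1 week. Label 8 then holds week 12 instead of week 8, and later labels are 4 weeks out. A missed QLQ-C30 moves every later label by 4 weeks.

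**3. Average shift.** Assume forms are missed independently with probability p (the documents give no rate). The k-th completed form then falls on average in slot k/(1 − p). QLQ-C30 slot s is week 4s. QLQ-LC13 slot s is week 4s − 24 from slot 8 on. For label 12:

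| p | QLQ-LC13 (scheduled week 24) | QLQ-C30 (scheduled week 48) |
|---|---|---|
| 10% | 4 × 13.33 − 24 = 29.3 | 4 × 13.33 = 53.3 |
| 20% | 4 × 15 − 24 = 36.0 | 4 × 15 = 60.0 |

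With 10% missing in one arm and 20% in the other, the arms differ by 6.7 weeks at this label. With equal rates the expected difference is 0.

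**4. Effect on the treatment contrast.** This was simulated with no true treatment effect and an assumed mean change of −12(1 − exp(−t/8)) + 0.10 × max(t − 24, 0), t in weeks. Labels were kept while more than 25% of patients contributed, in line with the SAP's rule on excessive missing data. The false equal-weight average difference at 10% against 20% missing was:

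| | QLQ-LC13 | QLQ-C30 |
|---|---|---|
| No stopping at progression | 0.33 | 0.42 |
| Stopping at progression, exponential, median 10 months (protocol placebo assumption) | 0.19 | 0.32 |

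The second row is closer to the plan, because the model stops at progression, death or 24 months. The largest single-label difference was about 1 point. At 20% against 20% the average was 0.00.

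**The case against.** The best defence is that the SAP numbers visits and does not say completed assessments. A reader might infer that any missed diary necessarily moves later data. The documents do not say so, and several features point the other way. Table 8 stays within 4 days of schedule. The improvement example in SAP 3.3.1.3 and the deterioration example in Appendix B both leave a missed visit in its own numbered place. The excessive-missingness rule and the option of multiple imputation also sit more naturally with fixed slots.

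A reader might also infer that the two arms are compared at different times. That does not follow from the rule alone. Both arms share one schedule set from randomization, and with equal missingness they remain aligned in expectation. No document suggests that missingness will differ by arm. The trial is double-blind, sites are advised to call patients when compliance drops below 90%, and compliance is tabulated by arm and time point, so a difference would be seen.

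All of this limits the size and certainty of the effect. It does not supply the missing rule. The other PRO derivations show missed visits explicitly, this section does not, and the stated reason for the variable does not match the protocol's schedule.

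**Conclusion.** The point holds as a minor one. The plan specifies a numbering method that is not tied to scheduled weeks, is silent on missed assessments, and rests on discontinuation visits for which the protocol schedules no PRO. A shift occurs only if completed assessments are numbered. Bias between arms needs, in addition, missingness that differs by arm. On both conditions, and on the assumed trajectory, 10% against 20% missing gives an average bias of about 0.2 to 0.4 points against the 10-point threshold for meaningful change. With equal missingness the cost is blurred visit-specific estimates. The endpoints are supportive secondary ones without multiplicity adjustment and outside the multiple testing procedure, so neither dual primary conclusion is affected.

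**What to change.** In SAP 4.2.11.1, define the mixed model's visit factor as the scheduled analysis visit from the SAP 4.1.2 windows, using study day from randomization. State that a missed assessment stays missing at its own label. Delete the sequential generic visit and Table 8.

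If the sponsor prefers to keep Table 8, add that labels follow scheduled weeks and say which slot a discontinuation assessment fills.

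Either version is a change of SAP wording that needs no new data. The first also simplifies programming, because the windows and the rules for several ePRO records in one window already exist.

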Durvalumab immunogenicity assessment (ADA sampling) to identify ADA responses i			X		X				8.5
Tremelimumab immunogenicity assessment (ADA sampling) to identify ADA responses j			X		X				8.5

					Time since	e last dose	of IP		
	Day (±3)			Week (	±1 week)			48 weeks and every	
Evaluation	30	8	12	16	24	32	40	8 weeks (±2 weeks) until study termination or death	For details, see Section
Whole blood for gene expression (PaxGene-RNA tubes, not applicable for China)	X	X							8.8
Circulating soluble factors (including TMB; plasma, not applicable for China)	X	X							8.8
EORTC QLQ-LC13 (by e-device) k		Weekly (±1 day on weeks 1, 2, 3, 5, 6 and 7, and ±3 days on weeks 4 and 8) for the first 8 weeks from randomization and then every 4 weeks (±3 days) relative to randomization until study termination or PFS2 or death							
EORTC QLQ-C30 (by e-device) k	Every 4	weeks (±3	3 days) rela	tive to rand	lomization	until study	termination	n or PFS2 or death	8.1.3
PRO-CTCAE (by e-device) k				hen every 4		days) rela		4, 8 and 12) for the first omization until study	8.1.3
PGIS (by e-device) k	Every 8	weeks (±3	3 days) rela	tive to rand	lomization	until study	termination	n or PFS2 or death	8.1.3
EQ-5D-5L (by e-device) k	Every 8	weeks (±3	3 days) rela	tive to rand	lomization	until study	termination	n or PFS2 or death	8.1.3
Health resource use module (HOSPAD)					X			X m	8.9
Tumor assessment (CT or MRI) (RECIST 1.1) 	On-study tumor assessments occur q8w ±1w for the first 72 weeks (relative to the date of randomization), followed by q12w ±1w until up to 96 weeks relative to the date of randomization, and then q24w ±1w thereafter (relative to the date of randomization) until RECIST 1.1-defined radiological progression, plus one follow-up scan no earlier than 4 weeks later and no later than the next regularly scheduled imaging visit. This on-study schedule MUST be followed regardless of any delays in dosing. Additional scans to be completed per standard practice post-progression. Tumor assessments up to progression may continue after the PFS analysis and up to the end of the study						8.1		

For women of childbearing potential only. A urine or serum pregnancy test is acceptable.

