1.3 Number of Subjects

The study will plan to enroll approximately 965 patients globally in order to randomize approximately 724 patients to 1 of 3 treatment groups: durvalumab monotherapy (approximately 262 patients), placebo (approximately 262 patients), or durvalumab + tremelimumab combination therapy (approximately 200 patients) over a period of approximately 38 months. Initially, patients will be randomized 1:1:1 to the 3 treatment groups. Following implementation of CSP Version 4, once 600 patients have been randomized, a further 124 patients will subsequently be randomized 1:1 to durvalumab monotherapy or placebo until a total of approximately 724 patients have been randomized.

The study has dual primary objectives which are to assess the efficacy of durvalumab monotherapy compared to placebo in terms of PFS per RECIST 1.1 as assessed by BICR, and OS.

The primary PFS analysis will occur at the earliest of:

- 1. When approximately 370 PFS BICR events have occurred (70.6% maturity) in the durvalumab monotherapy and placebo treatment groups
- 2. At OS-IA2, if OS-IA2 is statistically significant (durvalumab monotherapy vs placebo)
- 3. Approximately 36 months after the last patient randomized

If the true PFS HR is 0.65 for durvalumab monotherapy versus placebo, with 370 PFS BICR events, the study will have approximately 90% power to demonstrate a statistically significant difference in PFS between durvalumab monotherapy and placebo, with an overall 2-sided significance level of 0.5%. The true HR of 0.65 translates to a 5.4 month benefit in median PFS over 10 months on placebo if PFS is exponentially distributed. The smallest treatment difference that would be statistically significant is a HR of 0.743 (Critical value (CV)). At this time, approximately 309 PFS BICR events are also expected to have occurred in the durvalumab in combination with tremelimumab and placebo treatment groups. A recruitment period of approximately 38 months was assumed in the CSP for the primary PFS analysis.

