4.1.2 Visit window for safety and PRO assessments

Time windows will need defining for any presentations that summarize values by visit. The following conventions should also apply:

- The time windows should be exhaustive so that data recorded at any time point has the potential to be summarized. Inclusion within the time window should be based on the actual date of assessment and not the intended date of the visit. For laboratory assessments, if date of assessment is missing, visit date will be used.
- All unscheduled visit data should have the potential to be included in the summaries.
- The window for the visits following baseline will be constructed in such a way that the upper limit of the interval falls half way between the two visits (the lower limit of the first post-baseline visit will be Day 2). If an even number of days exists between two consecutive visits, then the upper limit will be taken as the midpoint value minus 1 day.

For example, the visit windows for vital signs data (with 4 weeks between scheduled assessments) are:

- Day 29, visit window 2-42
- Day 57, visit window 43 70
- Day 85, visit window 71 − 98
- Day 113, visit window 99 126

Note that visits up to 28 days after the last dosing date will be considered as being on treatment for the purposes of visit windowing and may be assigned to an ontreatment visit. Visits after this will be considered as follow-up and may be assigned accordingly.

- For summaries showing the maximum or minimum values, the maximum/minimum value recorded on treatment will be used (regardless of where it falls in an interval).
- Listings should display all values contributing to a time point for a patient.
- For non-EPRO visit based summaries:

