Symptom, functional and GHS/QoL improvement rates will be analyzed by comparing between treatment groups using a logistic regression model adjusting for the same factors as the PFS endpoint. The results of the analysis will be presented in terms of an odds ratio together with its associated profile likelihood 95% CI and p-value (based on twice the change in log-likelihood resulting from the addition of a treatment factor to the model). The odds ratio and 95% CI for each scale/item will be presented graphically on a forest plot. If there are very few responses in 1 treatment group, a Fisher's exact test will be considered.

Change from baseline

Summaries of original and change from baseline values of each symptom scale/item, the GHS/QoL score, and each functional domain will be reported by assessment timepoint for each treatment group. Graphical presentations may also be produced as appropriate. Summaries of the number and percentage of patients in each response category at each assessment timepoint for each ordinal item (in terms of the proportion of patients in the categories of improvement, no change, and deterioration as defined in Table 6) will also be produced for each treatment group.

A summary of compliance rate and evaluability rate will be provided for each treatment group, by assessment time point and also for overall. The summary will be provided for the FAS, combination analysis set, and patients who have discontinued treatment.

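### Does giving every visit equal weight in the patient-reported outcome mixed model wrongly tilt the QLQ-LC13 averages toward the first eight weeks?

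*SAP*

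**What the plan says.** SAP 4.2.11.1 says that the mixed-model analysis is to "compare the average treatment effect from the point of randomization until PD, death or 24 months", unless data are missing for more than 75% of randomized patients in any arm. It then defines the overall adjusted mean as the "average treatment effect over visits giving each visit equal weight". Visit is a categorical effect and interacts with treatment.

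The two questionnaires have different calendars. Protocol 1.1, Tables 1 and 2, has the QLQ-LC13 weekly "for the first 8 weeks from randomization and then every 4 weeks (±3 days) relative to randomization until study termination or PFS2 or death". For the core questionnaire, SAP Appendix B states: "The scheduled visit assessments and visit windows for the QLQ-C30 are 4 weekly (±3 days) relative to randomization". Dyspnea, cough and chest pain come from the LC13. Global health status/QoL, physical and role functioning, fatigue and appetite loss come from the C30.

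On the visit factor, SAP 4.2.11.1 says that "to include the discontinuation and follow up visits, a generic visit variable will be derived for each patient", numbered in sequence. SAP 4.1.2 gives the windowing convention for by-visit summaries: "Inclusion within the time window should be based on the actual date of assessment and not the intended date of the visit". It counts study days for patient-reported data from randomization.

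**The concern.** A reader told that a number is the average effect from randomization to 24 months may take it as an average over that time. For the LC13 scores it is not: the first eight weeks are sampled four times as densely as the rest, and equal visit weights pass that density straight into the estimate. The C30 scores, likely to be tabulated alongside, have no such tilt. If the early treatment effect differed from the later one, the single LC13 difference, with its confidence interval and p-value, would be pulled toward the early effect, and the two sets of scores would cover the 24 months differently.

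The generic visit number raises a smaller doubt. The diary schedule runs from randomization and has no separate discontinuation assessment, and the SAP does not say whether a missed diary keeps its number.

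**Working it through.** The documents give no visit count or early share for this model, so there is no stated figure to reproduce.

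**Inputs.** A month is 30.4375 days (SAP 4.1), so 24 months = 730.5 days = 104.4 weeks. The schedules are as quoted. For follow-up to progression, SAP 1.3 assumes a "5.4 month benefit in median PFS over 10 months on placebo if PFS is exponentially distributed", which gives medians of 10 and 15.4 months.

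**Visit counts to week 104**

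- LC13: weeks 1-8 (8 visits) plus weeks 12, 16, ..., 104 (24 visits) = 32. Share of weeks 1-8: 8/32 = 25.0%.
- C30: weeks 4, 8, ..., 104 = 26 visits. Share of weeks 1-8: 2/26 = 7.7%.
- Time: 8/104 = 7.7%.
- Mean visit week: LC13 (36 + 1392)/32 = 44.6; C30 54.0.

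**Effect of the missing-data rule.** The SAP does not say exactly how the rule operates; I read it as ending the averaging period. With a 10-month exponential median and full diary completion, the placebo arm falls to 25% progression-free at 20 months = 20 × 30.4375/7 = week 87, so the last retained visit is week 84. The shares become 8/27 = 29.6% for LC13 and 2/21 = 9.5% for C30. With an assumed 80% completion the last visit is week 72 and the shares are 8/24 = 33.3% and 2/18 = 11.1%. The early share is therefore 25% or somewhat more.

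**Distance from a time-weighted average.** Suppose one effect in weeks 1-8 and another afterwards, differing by a gap g. The difference between the two averages is (early share with equal weights − early share with time weights) × g.

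- 4-weekly grid: (0.250 − 0.077)g = 0.173g.
- Midpoint-interval weights (early share 10/104 = 0.096): (0.250 − 0.096)g = 0.154g.
- Calendar ending at week 84, 4-weekly grid: (0.296 − 0.095)g = 0.201g.

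On the full calendar, assumed gaps of 2.5 and 5 points give 0.38-0.43 and 0.77-0.87 points. With the week-84 cut they give up to 0.50 and 1.0. A linear drift of 5 points over 24 months gives 5 × (54.0 − 44.6)/104 = 0.45 on the grid and 5 × (52.0 − 44.6)/104 ≈ 0.35 with midpoint weights. A constant effect gives 0.

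**Cost of reweighting.** I took 262 patients per arm, data to progression under the SAP's medians, and assumed diary completion of 80-100%. The standard error of the equal-weight difference is then about 0.057-0.076 SD, or 1.1-2.3 points for an assumed SD of 20-30. Moving to grid or interval weights multiplies it by 1.01-1.02 (compound symmetry), 1.04-1.06 (mixed) or 1.07-1.10 (autoregressive).

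**Break-even.** Take the time-weighted average as the target. Reweighting lowers mean squared error only if (shift factor × g)² exceeds SE²(r² − 1), where r is the standard-error ratio. With an assumed SD of 25:

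- Compound symmetry 0.5: SE = 0.0655 × 25 = 1.64 and r = 1.018, so g = 1.64 × 0.191/0.173 = 1.8 points.
- Autoregressive 0.9 per 4 weeks: SE = 0.0705 × 25 = 1.76 and r = 1.085, so g = 1.76 × 0.421/0.173 = 4.3 points.

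Across the cases tried, the break-even gap is roughly 1.3 to 4.3 points.

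**Visit numbering.** In SAP Table 8 both example patients are at day 43 at generic visit 6, although one discontinues after the first scheduled visit and the other after the fourth. The discontinuation visit takes a slot and the calendar stays aligned.

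**The case for a change.** The case for a change has substance. Protocol 9.5.1.9 makes this model the main analysis of the patient-reported measures, and three of the five symptoms named as primary come from the LC13. No text says the early weeks were meant to count more; the weighting is a by-product of the collection schedule. The missing-data rule enlarges the early share. Descriptive tables can reveal a time-varying effect but cannot correct the overall estimate. A revised contrast would need one line of code and no new data.

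The arithmetic stands in full, and so does the observation that the LC13 average is early-weighted. What does not follow is that the plan is wrong. The sentence about 24 months sets the follow-up window; the weighting sentence defines the average. The shift is therefore a distance to a different estimand, not bias against the stated one. Time-varying effects will be visible: the model has a treatment-by-visit term, and the raw and change-from-baseline summaries for symptom scales, global health status and "each functional domain will be reported by assessment timepoint for each treatment group". Each score is modelled separately, and no analysis pools or compares LC13 with C30 differences.

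The numbering point is missing detail that a programmer can settle from Table 8 and the date-window convention in SAP 4.1.2. That section sets a rule but does not tabulate windows for the diaries.

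**Conclusion.** No change is needed. Weeks 1-8 carry 25% of the LC13 overall estimate on the full calendar, and about 30% if visits after week 84 drop out under the 10-month exponential placebo median with full completion. The corresponding C30 shares are 7.7% and 9.5%. This follows from an explicitly stated, legitimate estimand.

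On the full calendar, assumed early-to-late gaps of 2.5 to 5 points shift the estimate by 0.38 to 0.87 points, less than one standard error. For scale, the documents treat a within-patient change of 10 points as clinically meaningful. Time-weighting would cost about 1-10% in standard error and put more weight on visits where, at week 104, only about 19% of placebo and 34% of durvalumab patients would still be progression-free. It pays only if the gap exceeds roughly 1.3 to 4.3 points, and the documents neither support nor exclude such a gap. The gaps, SDs, covariances and completion rates are assumptions; the visit counts are not.

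Protocol 9.5.1.9 treats these endpoints as supportive, without multiplicity adjustment, so PFS and OS inference is untouched. A statistician who wishes may note the early weighting when reporting, or show a 4-weekly contrast over the retained visits as a sensitivity result, but the plan is sound without either.
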